Comparison of hydro-dissection versus ultrasonic aspirator in division of liver parenchyma in laparoscopic resection

Lap Liver Study

NCT03208192

20/02/2017

Study Design – Lap Liver Resection

Title of the study: comparison of water-jet dissector with ultrasonic aspirator in division of liver parenchyma in laparoscopic resection

Background: until now, there is no agreement about the safest and feasible method for liver parenchyma transection during laparoscopic liver resection.

Study design: prospective, randomized, single-center

The purpose of the study: comparison of short-term results of two methods of parenchyma liver transection during laparoscopic liver resection

Material and Methods: two groups will be compared.

Group 1: liver resection using a bipolar dissector (Erbe), ultracision harmonic scalpel (Ethicon) and water-jet dissector (ERBEJET 2).

Group 2: liver resection using a bipolar dissector (Erbe), ultracision harmonic scalpel (Ethicon), and ultrasonic aspirator (Misonix/SonaStar Ultrasonic Surgical Aspiration System)

Indication laparoscopic liver resection.

- Benign liver tumors (hemangioma, focal nodular hyperplasia, hepatocellular adenoma, biliary cystadenoma):
 - lesions of 7 cm or more and clinical manifestation with complaints of abdominal pain due to physical activity or body position.
 - Unresolved suspicion for malignancy
- Hydatid echinococcosis
- Malignant tumors (colorectal cancer metastases in the liver, hepatocellular carcinoma, intrahepatic cholangiocellular carcinoma, gallbladder cancer T1b-3NxM0

For enlargement of the groups patients with Hydatid echinococcosis are included if total pericystectomy is performed. The surgery in those cases does not differ from liver resection for benign tumors.

Inclusion Criteria:

- Patients with benign lesions (hemangioma, focal nodular hyperplasia [FNH], hepatocellular adenoma, biliary cystadenoma, hydatid echinococcosis [only with total pericystectomy]) and malignant tumors (colorectal cancer metastases in the liver [CRLM], hepatocellular carcinoma [HCC], intrahepatic cholangiocellular carcinoma, gallbladder cancer T1b-3NxMo without invasion into bile ducts and adjacent organs), which involves laparoscopic segmental or major resection of the liver.
- Gender: both, male and female
- Minimum age 18 years
- Maximum age: 80 years
- ASA physical status I-IV
- BMI up to 40 kg/m²

It is mandatory to estimate the complexity of laparoscopic liver resection by calculating the difficulty index proposed by Go Wakabayashi (2014) and modified in 2016 (attachment 1). As the difficulty index includes the type of liver resection (partial resection, segmentectomy, and sectionectomy), the size and topography of the tumor, its proximity to the large vessels of the liver, the presence and stage of liver cirrhosis (CTP), all patients in each group will be divided into four subgroups according to the complexity of liver resection: low, intermediate, advanced and expert.

The comparison will be conducted between groups 1 and 2 according to difficulty of liver

resection.

Comparative analysis should include following intraoperative and postoperative factors

Primary endpoint:

Intraoperative blood loss - absolute measurement of blood loss in relation to resection size (ml/cm²)

Absolute blood loss will be calculated as the amount of blood (collected only during the parenchyma resection) in suction the container after the subtraction of all irrigating fluids and weighing operative sponges.

Secondary endpoints:

Intraoperative factors:

1. Blood loss relative to total blood volume (%) (attachment 2)
2. Duration of liver parenchyma transaction.
3. Necessity to apply the Pringle maneuver.
4. Number of Pringle maneuver applications.
5. The total duration of Pringle maneuver.
6. Duration of the longest application of Pringle maneuver
7. Number of patients needed for banked blood transfusion
8. Number of bank blood units needed for transfusion
9. Rate of conversion to hybrid (with upper midline incision of 10 cm long), open or robotic surgery
10. Open/lap surgery before laparoscopic procedure

Postoperative factors:

1. Morbidity according to Clavien-Dindo classification (it is advisable to activate complications class II-V), as shown in attachment 3.
2. Duration of hospital stay

Bile leakage will be classified in severity according to the international study group for liver surgery (A,B,C) (attachment 4).

Since the difficulty index does not take into account the number of liver lesions (and, in fact, needs to be calculated for each of the multiple lesions), only resection of the liver lesion with the highest difficulty index must be considered when comparing groups (especially for the liver parenchyma transection).

Flow chart and CRF are attached.

- A Grade B bile leakage requires active therapeutic intervention but is manageable without relaparotomy.
- Grade C bile leakage, relaparotomy is required.

Source:

Koch et al, Bile leakage after hepatobiliary and pancreatic surgery: A definition and grading of severity by the International Study Group of Liver Surgery. *Surgery* Volume 149, Issue 5, May 2011, pages 680-688

<http://www.sciencedirect.com/science/article/pii/S0039606010006781>

Comparison of hydro-dissection versus ultrasonic aspirator in division of liver parenchyma in laparoscopic resection

Lap Liver Study

NCT03208192

15/05/2020

Statistical Analysis Plan

The samples size of 60 patients was calculated for 90% statistical power. Randomization in each arm was performed using envelopes. Continuous data presented as median values were compared using the Mann–Whitney U test. Two-tailed Fisher's Exact Test was used for comparing categorical variables. A P-value of less than 0.05 was considered statistically significant. SPSS version 23.0 (IBM SPSS, Inc., Chicago, IL) software package was applied for data analysis.

Inclusion criteria were benign liver tumors (hemangioma, focal nodular hyperplasia, hepatocellular adenoma, hydatid echinococcosis [only with total pericystectomy]) and malignant tumors (colorectal cancer metastases, hepatocellular carcinoma, intrahepatic cholangiocarcinoma). In addition to the standard criteria, specific exclusion criteria were liver cirrhosis and the inability to provide standard conditions for the bleeding prevention (high central venous pressure, fragile liver parenchyma due to severe steatosis and other advanced drug-induced changes). Primary endpoint was ratio of blood loss to resection area (mL/cm²). I

An addition to the exclusion criteria specified in the design of the study, the latter were expanded due to the following position: Intraoperative incidents not related to liver resection (strong adhesions leading to organ damage or insufficient vascular control, impossibility to decrease CVP due to patient condition, changing the operation plan due to intraoperative findings like invasion into adjacent organs or multiple lesions, equipment problems).

All operations were performed by a single surgeon.

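### The SAP drops the protocol's comparison by difficulty index, so its primary test forgoes whatever precision that baseline score could add

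*SAP*

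**What the plan says.** Protocol, section Difficulty Index: "It is mandatory to estimate the complexity of laparoscopic liver resection by calculating the difficulty index". The same section says that "all patients in each group will be divided into four subgroups according to the complexity of liver resection: low, intermediate, advanced and expert", and then that "The comparison will be conducted between groups 1 and 2 according to difficulty of liver" resection. After the list of postoperative factors, the protocol adds that for patients with several lesions "only resection of the liver lesion with the highest difficulty index must be considered when comparing groups". The Exclusion Criteria also use the index, which implies that it is scored before surgery.

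SAP, first paragraph: "Continuous data presented as median values were compared using the Mann–Whitney U test" and "Two-tailed Fisher's Exact Test was used for comparing categorical variables". No stratum, covariate, subgroup or difficulty index appears anywhere in the SAP. On size it says "The samples size of 60 patients was calculated for 90% statistical power", without an effect size or SD and without saying whether 60 is the total or the number per arm. Allocation is by envelope, and no stratification by difficulty is mentioned.

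**The concern.** The protocol announces a comparison by difficulty and the SAP supplies no method for it. The SAP also does not say that the comparison was dropped or made descriptive. Read plainly, the primary analysis is one pooled Mann–Whitney test of mL/cm².

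Two things are at stake. A reader cannot tell whether the comparison by difficulty is primary, secondary, descriptive or abandoned. And if difficulty predicts blood loss per cm², a test that ignores it leaves explainable variation in the error term. In a trial this small, and with no stratification described, the arms may also differ in difficulty by chance with nothing in the analysis to account for it.

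**Working it through.** **Inputs from the documents.** N = 60, 90% power, significance level 0.05. The SAP states two-sidedness only for Fisher's test.

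**Assumed, because the documents are silent.** Two-sided Mann–Whitney test; 1:1 simple randomisation; everyone randomised is analysed; normal outcome; index distributed N(6, 2.5), rounded and held to 0–12; levels cut at 0–3, 4–6, 7–9 and 10–12; share of outcome variance explained by the index (R²) from 0 to 40%.

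**The SAP's own figure.** N = 60 cannot be reproduced without an effect size, so I solved for the difference it implies:

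d = (1.960 + 1.282) × √(2/n), divided by √0.955 for Mann–Whitney efficiency.

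- 60 in total (n = 30 per arm): 3.242 × 0.2582 = 0.837, or 0.856 for Mann–Whitney.
- 60 per arm: 3.242 × 0.1826 = 0.592, or 0.606 for Mann–Whitney.

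**Expected gain by formula.** Adjustment multiplies the residual SD by √(1 − R²), so power = Φ(3.242/√(1 − R²) − 1.960). At R² = 0.09 this is Φ(3.398 − 1.960) = 92.5%; at R² = 0.25, Φ(3.743 − 1.960) = 96.3%; at R² = 0.36, 98.2%. These are for linear ANCOVA at d = 0.837, against 90.0% unadjusted.

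**Simulated power, 30 per arm, d = 0.86, 40,000 trials per row.** Rank-ANCOVA regresses the outcome rank on arm and on the rank of the index, and tests the arm term.

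| R² | Mann–Whitney | Rank-ANCOVA | Van Elteren, 4 levels |
|---|---|---|---|
| 0 | 88.7% | 88.6% | 85.8% |
| 0.05 | 88.8% | 90.0% | 87.3% |
| 0.10 | 88.4% | 91.1% | 88.5% |
| 0.20 | 88.5% | 93.9% | 91.7% |
| 0.30 | 88.6% | 96.3% | 94.3% |
| 0.40 | 88.3% | 98.1% | 96.6% |

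If 60 means per arm (d about 0.61, 20,000 trials per cell), rank-ANCOVA changes power by about 0, +3, +5, +7 and +9 points at R² = 0, 10, 20, 30 and 40%.

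**Type I error, 30 per arm, 80,000 null trials.** Overall: Mann–Whitney 4.7–4.9%, rank-ANCOVA 4.9–5.0%, van Elteren 4.8–5.0%.

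**Chance imbalance.** Under N(6, 2.5), about 42% of patients score 7 or more: P(Z > (6.5 − 6)/2.5 = 0.2). With 30 per arm, the arms then differ by 6 or more such patients (6/30 = 20 points) in about 15% of trials; with 60 per arm, a 20-point difference occurs in about 3%. Mann–Whitney false-positive rates at 30 per arm:

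| R² | In the 15% | In the other 85% |
|---|---|---|
| 0 | 4.8% | 4.7% |
| 0.10 | 6.5% | 4.5% |
| 0.20 | 8.9% | 4.1% |
| 0.30 | 10.4% | 3.7% |
| 0.40 | 12.8% | 3.4% |

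The rates average back to about 5%: at R² = 0.40, 0.15 × 12.8 + 0.85 × 3.4 = 4.8%. Rank-ANCOVA stays at about 5% in both columns.

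**Separate tests by level.** 60/4 = 15 patients per level on average, or 7 to 8 per arm. Four such tests would lose power; any gain comes from one adjusted test.

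**The case against.** The strongest reply is that the loss is hypothetical. No document links the index to mL/cm², and the larger gains need R² of 20–40%, a correlation of about 0.45–0.63. The endpoint is already divided by resection area, and in the SAP "specific exclusion criteria were liver cirrhosis" among other conditions; both may weaken the link. At R² of 0–5% the gain is 0–1 point. An unadjusted primary test in a small randomised trial is a legitimate choice. This stands as a limit on the size of the point. But the index also scores tumour location and proximity to large vessels, which area does not capture, and rank-ANCOVA costs almost nothing if the index proves uninformative.

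Second, the SAP is written in the past tense, so outcomes may already have been known. In that case a change of primary test is not open and primary power gains nothing. This stands, and the fix has a separate branch for it.

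Third, the protocol speaks of four subgroups, not of covariate adjustment. Van Elteren follows that wording more literally, and it costs about 3 points when the index is not prognostic. That is correct. The near-zero cost applies to rank-ANCOVA only.

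Fourth, the scoring time is not stated, the preoperative examination list omits the index, and the index contains a hybrid-approach item while conversion to hybrid is an outcome. Use as an eligibility criterion implies preoperative scoring but does not prove that the recorded value was fixed before allocation. This stands as a condition on the fix.

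Finally, the SAP's added exclusions for intraoperative incidents may act after allocation, and then no test is guaranteed 5%. That is a separate problem and affects either test.

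**Conclusion.** The concern holds. The protocol promises a comparison by difficulty; the SAP neither carries it out nor says what became of it. The pooled Mann–Whitney test is valid overall, so the cost is in precision and in consistency between the documents. Under the stated assumptions, rank-ANCOVA on the index changes power by about 0 to +10 points as R² goes from 0 to 40%, and by at most +3 up to R² = 10%. Where the trial lies in that range cannot be known from the documents. The higher conditional false-positive rates under imbalance rest on assumed simple randomisation and an assumed score distribution; they do not mean that the overall error rate is inflated. The change should be made, but the trial's validity does not depend on it.

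**What to change.** **If outcomes had not been seen when the SAP was written:**

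- Name rank-ANCOVA of mL/cm² on arm and the 0–12 index as the one primary test. Van Elteren across the four levels is an acceptable alternative, with the cost noted above.
- Use the index scored before allocation, on the planned approach and the highest-scoring lesion.
- Report the shift in mL/cm² with a 95% interval from inverting the same test, so that interval and p-value cannot conflict. In simulation this interval covered 93.8–95.9%. With a normal outcome, its median width was 1.05 SD at R² = 0 and 0.83 SD at R² = 0.4, against 1.06–1.08 SD for the unadjusted Hodges–Lehmann interval. If a Hodges–Lehmann interval is also shown, label it unadjusted and descriptive.
- Keep Mann–Whitney as a sensitivity analysis, and show the four levels descriptively without separate tests.

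The cost is SAP wording, one degree of freedom, a short script for the interval, and at most about 1 point of power if the index is unrelated to the outcome. No new data are needed, provided the score on file was fixed before allocation.

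**If outcomes had been seen:** keep Mann–Whitney as primary, add the difficulty-adjusted analysis labelled post hoc and supportive, and state that the protocol's comparison by difficulty is descriptive. The cost is one extra analysis, with no gain in primary power.

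In either case the SAP should also say what the comparison by difficulty means for the outcomes assigned to Fisher's test, since the protocol does not confine it to the primary endpoint.
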